10.3 Adverse events (AEs)

Any AE occurred during the study period will be included in AE summary tables as described in [Section 10.1](#), i.e., AEs occurred in run-ins, double-blind period, and SAEs up to one-month after the study completion.

The incidence of treatment-emergent adverse events (new or worsened) will be summarized by primary system organ class, preferred term, severity, and relationship to study drug according to the Medical Dictionary for Regulatory Activities (MedDRA).

The MedDRA version used for reporting the study will be described in a footnote.

Within each reporting phase (run-ins or double-blind, see [Table 10-1](#)), the following rules are applicable. If a subject reported more than one adverse event with the same preferred term, the adverse event with the greatest severity will be presented. If a subject reported more than one adverse event within the same primary system organ class, the subject will be counted only once with the greatest severity at the system organ class level, where applicable. Statistical analyses, which will only be performed for the double-blind or later phase, will include all post-baseline AEs up to and including the analysis cut-off (AEs up to the final visit and SAEs up to 30 days after the final visit for each patient) irrespective of how long after the last day of study treatment they occurred.

The number and percentage of subjects reporting any adverse event during each reporting phase will be summarized by primary system organ class, preferred term and treatment. The most common adverse events reported ($\geq 1\%$ in any group for each preferred term in the SOC-PT table) will be presented in descending frequency according to its incidence in the LCZ696 group starting from the most common event.

Separate summaries, for each reporting phase (run-ins and double-blind), will be provided for study medication related adverse events, death, serious adverse event, other significant adverse events leading to study discontinuation and adverse events leading to dose adjustment.

Specific interested AEs will be summarized separately in addition to the above analysis. These specific interested AEs are: angioedema, hyperkalemia, hypotension, renal dysfunction, liver.

Due to the different durations in the two sub-run-in phases, besides providing percentages, the annualized exposure duration adjusted event rates will also be provided.

In addition to the above standard analyses, for the double-blind phase, analysis for time-to-first selected AEs by treatment group will be performed using Kaplan-Meier estimate. The annualized exposure duration adjusted event rates will also be provided.

10.4 Laboratory data

10.4.1 General laboratory data

Laboratory data will be summarized for each reporting phase as described before: Run-ins based on the VRS and LRS and double blind period based on the SAF.

The summary of laboratory evaluations will be presented for three groups of laboratory tests: hematology, serum chemistry and urinalysis, which include hemoglobin, hematocrit, RBC count, WBC count, platelet count, blood urea nitrogen (BUN), creatinine, estimated glomerular filtration rate (eGFR), total bilirubin, AST (SGOT), ALT (SGPT), alkaline phosphatase, sodium, potassium, chloride, calcium, phosphorus, total protein, albumin, and uric acid.

The eGFR is calculated according to the formula:

$$\text{eGFR (mL/min/1.73 m}^2\text{)} = 175 \times (\text{Serum creatinine}/88.4) - 1.154 \times (\text{Age}) - 0.203 \\ \times (0.742 \text{ if female}) \times (1.212 \text{ if black}),$$

where serum creatinine is in $\mu\text{mol/L}$ (SI unit) and age is non-rounded at the time of the laboratory sample in years.

Descriptive summary statistics (mean, median, standard deviation, min and max) for the change from baseline to each study visit will be presented. These descriptive summaries will be presented by laboratory test and treatment group. Change from baseline will only be summarized for subjects with both baseline and post baseline values and will be calculated as:

- change from baseline = post baseline value – baseline value

Note that baselines (for run-in and double blind phase) are defined in [Section 4](#).

In addition, shift tables will be provided for all parameters to compare a subject's baseline laboratory evaluation relative to the visit's observed value. For the shift tables, the normal laboratory ranges will be used to evaluate whether a particular laboratory test value was normal, low, or high for each visit value relative to whether or not the baseline value was normal, low, or high. These summaries will be presented by laboratory test and treatment group.

The number and percentage of subjects with clinically notable laboratory results after baseline will be presented. Clinically notable laboratory results, for those parameters where ranges are available, are given in [Table 10-3](#) below. For the calculation the denominator are based on the evaluable post-baseline subjects who did not have the notable abnormality at baseline from the central laboratory.

Table 10-3 Clinical notable criteria for selected laboratory tests
Hematology

RBC count	>50% increase, >20% decrease
Hemoglobin	>50% increase, >20% decrease
Hematocrit	>50% increase, >20% decrease
WBC count	>50% increase, >50% decrease
Platelet count	>75% increase, >50% decrease

Blood Chemistry

ALT (SGOT)	>150% increase
AST (SGPT)	>150% increase
BUN	>50% increase >14.28 mmol/L
Creatinine	>50% increase >136.8 µmol/L
Total bilirubin	>100% increase
CPK	>300% increase
Alkaline phosphatase	>100% increase
Sodium	>5% decrease
Potassium	>20% increase, >20% decrease ≥6.0 mmol/L >5.0 mmol/L <3.5 mmol/L
Chloride	>10% increase, >10% decrease
Calcium	>10% increase, >10% decrease
Uric acid	>50% increase

In the above table increase and decrease are defined as compared to the baseline value. Here baseline is defined as the run-in baseline for the run-in phases and the double-blind baseline for the double-blind phase.

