9.5.3 Safety variables

The safety and tolerability assessments are listed below:

- Identified and potential risks
- AEs and SAEs
- Sitting systolic, diastolic BP, and pulse pressure
- Heart rate
- Symptomatic hypotension
- Angioedema
- Hyperkalemia
- Renal dysfunction
- Other relevant laboratory values
- ECG changes

The assessment of safety will be based primarily on the frequency of AEs, SAEs, and laboratory abnormalities. Other safety data will be summarized as appropriate.

The incidence of treatment-emergent AEs (new or worsened) will be summarized by primary system organ class, preferred term, severity, and relationship to study drug. In addition, the

incidence of death, SAEs, and AEs leading to discontinuation will be summarized separately by primary system organ class and preferred term.

The incidence of AEs related to the identified and potential risks will be summarized by SMQ preferred terms.

Laboratory data will be summarized by presenting shift tables using extended normal ranges (baseline to most extreme post-baseline value), by presenting summary statistics of raw data and change from baseline values (mean, medians, standard deviations, ranges) and by the flagging of notable values in data listings. LFT categorical analysis will also be provided.

Data from other tests (e.g., ECG or vital signs) will be listed, notable values will be flagged, and any other information collected will be listed as appropriate.

Safety analyses will be performed based on the safety set. There will be no formal statistical inference analysis.

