The post-randomized treatment phase (usually after unscheduled, permanent study drug discontinuation) begins after last study drug intake + 1 day and ends on the date last seen (or vital status confirmed by indirect contact).

Double-blind (DB) phase (Randomized treatment epoch)

The double-blind phase is the combination of the randomized treatment phase and the post-randomized treatment phase.

Baseline for run-in phase

The treatment run-in baseline is defined as the last available measurement prior to or at time of Visit 101 or Visit 102, whichever is earlier. For some parameters, values may be only collected at screening (Visit 1). For them the treatment run-in baseline will be at screening.

Baseline for double blind phase

The baseline for the double blind phase is defined depending on the parameter considered. In general, the baseline for the double blind phase is defined as the last available measurement during the LCZ696 *run-in* phase and randomization (generally Visit 199 or Visit 201). For the parameters that are not designated to have measurements collected during the LCZ696 run-in or randomization, the run-in baseline may be used as the baseline for the double blind phase. The following parameters will have the double blind phase baseline at randomization visit:

NYHA class, HF signs and symptoms, vital signs, waist/hip circumference, eGFR, safety laboratory values, endpoints, 1st morning urine (sub-study patients only), lab assessments, patient global assessment (it is assumed that patients will assess their health status comparing to that at randomization), KCCQ scores and EQ-5D assessments and MMSE.

The following parameters will have their double blind phase baseline measured only at screening visit (Visit 1), i.e., prior or at Visit 101 or 102:

Height, (HF, diabetes, liver, and other) medical histories, demography, echocardiogram, and inclusion/ exclusion criteria.

NT-proBNP will be collected in all patients at Visits 1, 101/102 (whichever occurs first), 103, 199/201, 203 and 205. Additional biological markers will be collected in a subset of patients. For these biomarkers, the baseline will be defined as values at Visit 101 or 102, whichever occurs first.

Unscheduled visit

Only for the analysis of safety laboratory evaluation will unscheduled measurements be taken into account. For efficacy evaluations, measurements from unscheduled visits will generally not be used, unless specifically specified.

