Hepatotoxicity	
 1. Summary with frequency and percentage by treatment for patients with: 
 a. ALT or AST >3x ULN; b. ALT or AST >5x ULN; c. ALT or AST >8x ULN; d. ALT or AST >10x ULN; e. ALT or AST >20x ULN; f. ALT or AST >3x ULN and TB >1.5x ULN; g. ALT or AST >3x ULN and TB >2x ULN; h. ALT or AST >5x ULN and TB >2x ULN; i. ALT or AST >8x ULN and TB >2x ULN; j. ALT or AST >10x ULN and TB >2x ULN; k. ALT or AST >20x ULN and TB >2x ULN; l. ALP > 2 x ULN m. ALP > 3 x ULN n. ALP > 5 x ULN o. TB > 1.5 x ULN p. TB > 2 x ULN q. TB > 3 x ULN r. ALP > 3x ULN and total bilirubin > 2x ULN s. ALP > 5x ULN and total bilirubin > 2x ULN t. ALT or AST > 3x ULN and total bilirubin > 2x ULN and ALP =< 2x ULN u. (ALT or AST > 3x ULN and total bilirubin > 2x ULN and ALP =< 2x ULN) or reported Hy's Law case v. ALT or AST > 3x ULN and (nausea or vomiting or fatigue or general malaise or abdominal pain or (rash and eosinophilia)) w. TB >3x ULN and AST or ALT are ≤3 x ULN and alkaline phosphatase ≤1.5x ULN; x. AP >3x ULN and AST, ALT, TB are within normal range.

Risks	Analysis
	2. A cross-tabulation of baseline and worst post-baseline values by below, within and above normal range categories will be provided. Shift tables will be provided for the parameters AST, ALT, TB and AP.
Embryo-fetal toxicity/Lethality	Standard analysis
Neonatal/infantile toxicity through exposure from breast milk	Standard analysis
Statin drug-drug interaction	Standard analysis for patients who take statin during randomized treatment epoch (at baseline and post-baseline)
Malignancy	Standard analysis
Cognitive impairment	Standard analysis

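### SAP 10.4.1 replaces the protocol's worst-value laboratory shift table with by-visit tables, unrecorded and unexplained, so for some analytes the number of patients who ever left the normal range is not reported

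*SAP*

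**What the plan says.** Protocol 9.5.3 says laboratory data will be summarized with "shift tables using extended normal ranges (baseline to most extreme post-baseline value"), alongside summary statistics and flagged notable values. The same section makes the frequency of laboratory abnormalities, with AEs and SAEs, a primary basis of the safety assessment.

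SAP 10.4.1 says "shift tables will be provided for all parameters to compare a subject's baseline laboratory evaluation relative to the visit's observed value". It uses the normal laboratory ranges and sorts results as "normal, low, or high for each visit value relative to whether or not the baseline value was normal, low, or high". It then adds a separate count: "The number and percentage of subjects with clinically notable laboratory results after baseline will be presented", with the criteria in Table 10-3.

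The SAP keeps the worst-value form in two places. Under hepatotoxicity, Table 10-2 says "A cross-tabulation of baseline and worst post-baseline values by below, within and above normal range categories will be provided" and "Shift tables will be provided for the parameters AST, ALT, TB and AP". SAP 10.6 compares baseline ECG results with the maximum on-study result.

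On unscheduled samples, SAP Section 4 says "Only for the analysis of safety laboratory evaluation will unscheduled measurements be taken into account".

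The SAP's document history lists many changes but not this one. Neither document defines extended normal ranges.

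**The concern.** Two things differ between the documents: the value compared with baseline (each visit against the most extreme) and the range (normal against extended normal). The first changes the question answered. A by-visit table gives the share of patients abnormal at that visit. The protocol's table gives the share who were abnormal at any time after baseline. A patient who goes out of range once appears as shifted in one table and as normal in the others, and the tables cannot be added up into a count of patients.

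Unscheduled samples add to this. They are often taken because something looks wrong; Protocol Appendix 3, for example, calls for an immediate repeat sample when potassium exceeds 5.3 mmol/L. A table built on scheduled visits has no stated place for them, whereas a most-extreme-value table takes them in naturally.

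At stake is the completeness of the descriptive laboratory safety report. No efficacy result and no controlled error rate is affected.

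**Working it through.** **1. No figure to reproduce.** Neither document states an abnormality rate or any other number on this point. The check is a comparison of text, an inventory of what the SAP reports, and an illustration.

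**2. What the SAP reports per patient after baseline.** SAP 10.4.1 names 20 analytes. Set against Tables 10-2 and 10-3:

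| Analytes | Patient-level count after baseline | Worst-value shift on the normal range |
|---|---|---|
| AST, ALT, total bilirubin, alkaline phosphatase (4) | Multiples of the upper limit of normal, and percent increase | Yes |
| Potassium, creatinine, BUN (3) | Absolute thresholds and percent change | No |
| eGFR (1) | Declines of stated size | No |
| Sodium (1) | Decrease over 5% only; nothing for high sodium | No |
| Hemoglobin, hematocrit, RBC, WBC, platelets, chloride, calcium, uric acid (8) | Percent change only | No |
| Albumin, total protein, phosphorus (3) | None | No |

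4 + 3 + 1 + 1 + 8 + 3 = 20. Some patient-level count exists for 20 − 3 = 17. A worst-value normal-range shift exists for 4.

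**3. Why percent change is not a substitute.** A fall in hemoglobin from 12.5 to 10.2 g/dL is (12.5 − 10.2)/12.5 = 18.4%, which misses the criterion of more than 20%. With an assumed lower limit of 12 g/dL (the documents give no normal ranges), this patient has left the normal range and is not counted as notable.

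**4. How far a by-visit share can be from the ever-abnormal share.** Inputs:
- Mean follow-up is 3.375 years (SAP 13.3.4), which agrees with the accrual assumptions: 2 years 2 months + half of 2 years 5 months = 3.375. That is 3.375 × 52.18 = 176 weeks.
- Complete panels (Protocol 6.5.4 and Table 6-1) fall at Weeks 16, 48, 96 and 144 within that time, plus end of study, so k = 5. The abbreviated panels do not contain the uncovered analytes.
- Per-visit share p of 1%, 2% and 5%, and within-patient correlation ρ of 0, 0.5 and 0.8, are assumptions.

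Formulas: for independent visits, ever = 1 − (1 − p)^k. With correlation, ever = 1 − ∫ φ(u) · Φ((c − √ρ·u)/√(1 − ρ))^k du, where c = Φ⁻¹(1 − p).

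| p per visit | ρ = 0 | ρ = 0.5 | ρ = 0.8 |
|---|---|---|---|
| 1% | 4.9% | 4.0% | 2.8% |
| 2% | 9.6% | 7.5% | 5.2% |
| 5% | 22.6% | 16.6% | 11.7% |

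The ratio of ever-abnormal to per-visit share runs from 11.7/5 = 2.3 to 4.9/1 = 4.9. If the same patients are abnormal at every visit, it is 1.

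**5. What the by-visit tables alone can say.** The ever-abnormal share is at least the largest single-visit share and at most the sum over visits. At p = 2% and k = 5 that is anywhere from 2% to 5 × 2% = 10%. The published tables would not narrow this.

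**The case against.** The case for leaving the SAP as it is has real substance.

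- Protocol Section 9 calls itself a preliminary approach, so the SAP may refine it. Safety has no formal inference, and both arms get the same tables. All true, but a refinement that changes the quantity reported should be recorded, and this one is not. The SAP's introduction says the analysis follows the protocol's data analysis section.
- Most analytes already have a patient-level count. This stands and limits the point. Laboratory abnormalities that cause symptoms, are clinically significant or need therapy are also recorded as AEs (Protocol 7.1) and counted per patient (SAP 10.3).
- SAP 10.4.1 does not exclude unscheduled samples, Table 6-1 has an unscheduled-visit column, and the notable-result counts can include such samples. This also stands. A reader might infer that unscheduled values are dropped; the documents show only that the by-visit shift table gives them no stated place.
- Extended normal ranges are undefined. If they are wider than the normal ranges, the SAP's choice flags more values, so the change of range is not shown to conceal anything.

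A reader might also illustrate the loss with potassium, which is sampled more often and would give a larger ratio. That does not measure what is lost. Potassium is already counted per patient at >5.0, ≥6.0 and <3.5 mmol/L (Table 10-3) and at ≥5.5, >6.0 and >6.5 mEq/L (Table 10-2).

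**Conclusion.** The mismatch is real on both the comparison value and the range, and it is neither recorded nor explained. Its consequence is limited. There is no ever-abnormal count for three of the 20 named analytes, no count of high values for sodium, only percent-change counts for eight more, and no worst-value normal-range shift outside the four liver tests.

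The stronger reading, that the SAP hides how many patients became abnormal across the laboratory panel, is not supported: 17 of the 20 analytes have some patient-level count after baseline. Nor can it be said from the documents that the per-visit shares are small, since no prevalence is given.

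The ratio of about 2.3 to 5 rests on assumed prevalences of 1 to 5%, five complete panels and within-patient correlation from 0.8 down to 0. It falls to 1 under full persistence. It shows that the two quantities can differ materially and does not forecast this trial.

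**What to change.** In SAP 10.4.1:

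- Add, for every parameter with a normal range, shift tables from baseline to the lowest and to the highest post-baseline central-laboratory value in the phase, and state that unscheduled samples are included.
- Keep the by-visit tables as a supplement.
- Either define extended normal ranges or record that the normal laboratory ranges replace them, and enter the change in the document history.

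The cost is a few lines of SAP text and extra descriptive tables from data already held. Trial conduct, sample size and alpha are untouched.

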10.4.2 Specific laboratory data

Liver function test (LFT) data will be analyzed according to what specified in hepatotoxicity in [Table 10-2](#) in [Section 10.2](#).

Laboratory data related to renal impairment (serum creatinine, eGFR) will be analyzed according to what specified in renal impairment in [Table 10-3](#) in [Section 10.2](#).

10.5 Vital signs

Sitting systolic blood pressure, sitting diastolic blood pressure, sitting pulse rate and body weight will be summarized by treatment group and visit with standard summary statistics (mean, median, standard deviation, min, max), including changes from baseline. Baselines (run-in and double blind period) are defined in [Section 4](#). Graphical mean plots with 95% CIs for these vital signs will also be provided.

The descriptive summaries will be presented by vital sign and treatment group and visit. Change from baseline will only be summarized for subjects with both baseline and post-baseline values and will be calculated as:

- change from baseline = post-baseline value – baseline value

The number and percentage of subjects with clinically notable vital signs changes from baseline will be presented. Clinically notable vital sign results are provided in [Table 10-4](#) below.

Table 10-4 Clinically notable changes in vital signs

Vital Sign (unit)	Clinically notable criteria
Weight (kg)	decrease > 7% from Baseline increase > 7% from Baseline
Sitting systolic blood pressure (mmHg)	<90 and decrease from baseline of >20 >180 and increase from baseline of >20
Sitting diastolic blood pressure (mmHg)	<50 and decrease from baseline of >15 >105 and increase from baseline of >15
Pulse (bpm)	<50 and decrease from baseline of > 15 >120 and increase from baseline of >15

10.6 Electrocardiogram (ECG)

The following quantitative variables will be summarized: heart rate, QRS duration, and QTc. Summary statistics (n, mean, SD, min, Q1, median, Q3, max) for the change from baseline (Visit 201) in ECG intervals by visit and treatment will be provided. QTc categorical summary will also be provided (for both Fridericia and Bazett corrections) (for example, >500 ms, > 500 ms (with RBBB), > 500 ms (without RBBB)) and categorical summary for maximum change from baseline for QTc (> 60 ms, > 60 ms (with RBBB), > 60 ms (without RBBB)).

In addition, shift tables comparing baseline ECG results (normal, abnormal, not available, total) with the maximum on study result (normal, clinical significant, not available, total) will be provided for each variable. Clinically significant is defined if at least one abnormality: “atrial fibrillation, atrial flutter, LBB block, RBB block, pathological Q-waves, left ventricular hypertrophy, paced rhythm or other” is answered “yes”.

11 Resource utilization

Data relating to resource utilization will be used to describe medical resources used by the study participants. Mainly descriptive statistics of resources utilization data will be provided by treatment group.

12 Interim analyses

One interim analysis for efficacy is planned. The cut-off time for this interim analysis will be when about two-thirds of the target number of primary events have been reported and adjudication-confirmed, i.e., when approximately 1231 of composite of adjudication-confirmed hospitalizations for HFs and CV deaths are available. In the interim analysis, the analysis dataset will comprise all patients who were randomized before the cutoff date. Bonferroni multiplicity adjustment will be adopted for the statistical comparisons between treatments. An alpha of 0.001 (one-sided alpha) will be spent for the comparison of primary endpoint at the interim analysis and the rest of alpha (one-sided 0.024 for the current specified boundary) will be

utilized at the final analysis. In the interim analysis, the study may be stopped for superior efficacy only when the primary endpoint and CV death both are significant at level of 0.001 (one-sided).

If the study is stopped early for claiming superior efficacy at the interim analysis, the secondary endpoints will be tested using the same hierarchical testing procedure as described in [Section 9.3.2.1](#) before with an overall alpha level used for the primary endpoint at the interim analysis (one-sided alpha of 0.001 for the current specified boundary).

Interim safety assessments are planned to be performed every six months. No further alpha adjustment will be made for these interim safety assessments.

Interim analyses will be performed by an independent statistician who will not be involved in the trial conduct. The results will be reviewed by the independent DMC.

Investigators, Novartis employees, and others who are involved in the conduct of the trial will remain blinded to the treatment codes and interim analysis results until all monitoring decisions have been made and the database has been locked for the final analysis.

13 Power and sample size considerations

